11.2.1. All AEs

A summary of all AEs will be reported in a listing including:

- SOC
- PT
- Start Date/time

- End Date/time
- Severity
- Relationship to Medication (Y/N)
- Relationship to Study Procedure (Y/N)
- Seriousness (Y/N)
- Lead to Death (Y/N)

11.2.2. All TEAEs

A summary of TEAEs will be reported in the tables including:

- Number of all TEAE
- Number of patients with at least one TEAE

The summary of TEAEs will be broken down further in descending frequency by SOC and PT. A subject will be counted once if the subject reported one or more events in a given level of summarization.

11.2.3. Severity

Severity is classed as mild/moderate/severe (increasing severity). TEAEs with a missing severity will be classified as severe. If a patient reports a TEAE more than once within that SOC/PT, the TEAE with the worst case severity will be used in the corresponding severity summaries.

TEAE severity will be reported in a table in the same manner as outlined in 11.2.2.

11.2.4. Relationship to Study Medication

Relationship, as indicated by the Investigator, is classed as related or unrelated to study medication. TEAEs with a missing relationship to study medication will be regarded as related to study medication. If a patient reports the same AE more than once within that SOC/PT, the AE with the worst case relationship to study medication will be used in the corresponding relationship summaries.

TEAE relationship to medication will be reported in a table in the same manner as outlined in 11.2.2.

11.2.5. Relationship to Study Procedure

Relationship, as indicated by the Investigator, is classed as related or unrelated to protocol procedure. TEAEs with a missing relationship to study procedure will be regarded as related to study procedure. If a patient reports the same AE more than once within that SOC/PT, the AE with the worst case relationship to study medication will be used in the corresponding relationship summaries.

TEAE relationship to medication will be reported in a table in the same manner as outlined in 11.2.2.

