- Persistent or significant disability/incapacity;
- Congenital anomaly/birth defect;
- Considered significant by the investigator for any other reason.

Important medical events that may not result in death, be life-threatening, or require hospitalization may be considered serious adverse drug events when, based upon appropriate medical judgment, they may jeopardize the patient and may require medical or surgical intervention to prevent one of the outcomes listed in this definition.

Unexpected Adverse Event

An unexpected adverse event is an adverse event not previously reported or an adverse event that occurs with specificity, severity or frequency that is not consistent with the current IB.

Relationship to Study Drug

Investigators will be instructed to report their assessment of the potential relatedness of each adverse event to protocol procedure or study drug. The assessment of the relationship of an adverse event to the administration of the study drug is a clinical decision based on all available information at the time of the completion of the eCRF.

Intensity/Severity of an Adverse Event

In addition to assessing the relationship of the administration of the study drug to adverse events, an assessment is required, in order to determine the intensity (severity) of the event.

The following classifications should be used:

Mild:

A mild adverse event is an adverse event, usually transient in nature and generally not interfering with normal activities.

Moderate:

A moderate adverse event is an adverse event that is sufficiently discomforting to interfere with normal activities.

Severe:

A severe adverse event is an adverse event that incapacitates the subject and prevents normal activities. Note that a severe event is not necessarily a serious event; nor must a serious event necessarily be severe.

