Partial, could be on or after an injection date/time and within 48 hours post-injection	Known	
If stop date/time < flortaucipir (or florbetapir) injection date/time, then not TEAE
 
If stop date/time >= flortaucipir (or florbetapir) injection date/time, then TEAE

	Partial	
Impute stop date as latest possible date (i.e. 59 if minutes unknown or 23:59 if hours and minutes unknown; last day of month if day unknown or 31st December if day and month unknown), then:
 
If stop date/time < flortaucipir (or florbetapir) injection date/time, then not TEAE
 
If stop date/time >= flortaucipir (or florbetapir) injection date/time, then TEAE

AE ONSET DATE/TIME	AE STOP DATE/TIME	ACTION
	Missing	Assumed TEAE
Missing	Known	
If stop date/time < flortaucipir (or florbetapir) injection date/time, then not TEAE
 
If stop date/time >= flortaucipir (or florbetapir) injection date/time, then TEAE

	Partial	
Impute stop date as latest possible date (i.e. 59 if minutes unknown or 23:59 if hours and minutes unknown; last day of month if day unknown or 31st December if day and month unknown), then:
 
If stop date/time < flortaucipir (or florbetapir) injection date/time, then not TEAE
 
If stop date/time >= flortaucipir (or florbetapir) injection date/time, then TEAE

	Missing	Assumed TEAE

For the summarization of TEAEs by intensity, events recorded with missing intensity will be summarized as Severe.

For the summarization of TEAEs by seriousness, events recorded with missing seriousness will be summarized as Serious.

For the summarization of TEAEs by relationship to study drug or protocol procedure, events recorded with missing relationship will be summarized as Related.

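### SAP 11.2.5, on relationship to study procedure, reuses the medication wording of 11.2.4 in its repeat-event rule and its table sentence

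*SAP*

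**What the plan says.** SAP 11.2.5 has four working parts. Two use the variable in its heading:

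- Classification: the investigator's assessment "is classed as related or unrelated to protocol procedure".
- Missing values: "TEAEs with a missing relationship to study procedure will be regarded as related to study procedure".

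The other two use the drug variable:

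- Repeated events: "If a patient reports the same AE more than once within that SOC/PT", then "the AE with the worst case relationship to study medication will be used in the corresponding relationship summaries".
- Output: "TEAE relationship to medication will be reported in a table in the same manner as outlined in 11.2.2".

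The last two sentences also stand, word for word, in SAP 11.2.4 (Relationship to Study Medication), where they are correct.

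Other places bear on the intent. Protocol 7.7.2 has the assessment collected: "Investigators will be instructed to report their assessment of the potential relatedness of each adverse event to protocol procedure or study drug". SAP 11.2.1 includes a yes/no field for procedure relationship in the listing of all adverse events. SAP Appendix I 1.2 says: "For the summarization of TEAEs by relationship to study drug or protocol procedure, events recorded with missing relationship will be summarized as Related". Protocol 8.2 promises presentation by severity, relationship to treatment and seriousness, and does not mention procedure.

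**The concern.** A table program is written from the operative sentences of a SAP section. Here those sentences ask for the table that 11.2.4 already asks for, and no sentence in 11.2.5 asks for a table by procedure relationship.

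If the programmer infers that a procedure table is wanted and keeps the repeat-event rule as printed, the record that represents the subject is chosen on the wrong variable. A subject may have one record judged drug-related only and another, for the same term, judged procedure-related only. The rule keeps the first, and the subject enters the procedure table as unrelated.

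The rule can also work against the section's own conservative handling of missing data. A record with no procedure assessment is to count as procedure-related, yet it can be dropped in favour of a record that ranks worse on medication.

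The stake is descriptive safety reporting. Expanding the safety database is the study's secondary objective. The visit involves an intravenous catheter, an injection and a continuous brain scan, so separating tracer effects from procedure effects is a sensible thing to tabulate. No efficacy result depends on it.

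**Working it through.** The plan states no figure to reproduce. The check is a comparison of text followed by a small enumeration.

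**Text, side by side**

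| Element | SAP 11.2.4 | SAP 11.2.5 |
|---|---|---|
| Heading | medication | procedure |
| Classification | medication | procedure |
| Missing value counts as related to | medication | procedure |
| Repeats reduced by worst relationship to | medication | **medication** |
| Table named | medication | **medication** |

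The last two rows of the 11.2.5 column do not match the rest of that column.

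**Effect of the repeat-event rule**

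Inputs: each record carries D (related to drug, 0 or 1) and P (related to procedure, 0 or 1), after the missing-value rules have been applied. Consider a subject with two records of the same event in one system organ class and preferred term. There are 4 × 4 = 16 ordered patterns. The right entry in a procedure table is max(P1, P2). The rule as printed keeps the record with the larger D and reports its P.

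1. P1 = P2 in 2 × 4 = 8 patterns. Either record gives the right answer: 8 correct.
2. P1 ≠ P2 in the other 8 patterns, where the right answer is always related.
   - D1 = D2 in 2 × 2 = 4 of these. The rule does not say which record to keep: 4 undetermined.
   - D1 ≠ D2 in the remaining 4. In 2 the procedure-related record has the larger D and is kept: 2 correct. In 2 it has the smaller D and is dropped: 2 wrong.

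Totals: 8 + 2 = 10 correct, 2 wrong, 4 undetermined; 10 + 2 + 4 = 16.

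Because the right entry is a maximum, any error must show a procedure-related subject as unrelated; the reverse cannot happen. If the record is chosen by P instead, it carries max(P1, P2) by construction, and all 16 patterns are correct.

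With a single record in a class and term there is nothing to choose, and the rule has no effect.

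**Conditions for an error.** One subject must have the same event at least twice in the same class and term, with different procedure relationships, and the medication ranking must favour the other record or tie. Each tracer is given once (Protocol 5.2.1), the TEAE window is 48 hours after administration (SAP 11.2), the tracers are analysed separately (SAP 11), and about 30 subjects are planned (Protocol synopsis).

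**The case against.** The strongest reply is that this is a copying slip whose intended meaning is plain. The heading, the classification and the missing-value rule of 11.2.5 all name procedure, and a missing-value rule for procedure has no use unless a procedure summary is made. Appendix I 1.2 presupposes that summary. Producing the same medication table under two headings is an unlikely reading. This stands as evidence of intent. It does not supply the missing instruction, and it leaves the repeat-event rule as printed.

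A reader might go further and infer that procedure-related events are never correctly tabulated, or are hidden. The documents do not support that. SAP 11.2.1 lists every adverse event with its procedure relationship and no worst-case reduction. SAP 11.2.2 tabulates all TEAEs by class and term, whatever their relationship. No event disappears; at most, one attribute of a repeated event is wrong in one table.

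Three further limits stand:

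- Protocol 8.2 does not promise a procedure table, so even the literal reading breaks no protocol commitment on tabulation.
- SAP 11 plans no statistical comparison of safety data.
- The documents give no rate for catheter, injection-site or scan events, so how often such events would occur cannot be asserted. Events that begin after consent but before the injection are trial-emergent under Protocol 7.7.2, and lie outside a TEAE table even after the correction.

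**Conclusion.** The wording of 11.2.5 is wrong as written in two operative places. It should be treated as a drafting inconsistency with a real but narrow effect, not as a chosen method of analysis.

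The two defects differ in reach. The table sentence bears on every TEAE, because read literally no procedure table is specified; the intent can nevertheless be recovered from the same section and from Appendix I. The repeat-event rule bears only on repeats with discordant procedure relationships. Where the printed rule gives a definite wrong answer, it understates procedure-relatedness.

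The expected impact is small. That judgement rests on the planned size of about 30, one injection per tracer, and the 48-hour window. It also assumes that same-term repeats with discordant procedure assessments are uncommon, for which the documents give no rate. The enumeration assumes two records and binary assessments, as SAP 11.2.4 and 11.2.5 define them.

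**What to change.** Change two phrases in SAP 11.2.5:

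1. In the worst-case rule for repeated events, replace *study medication* with *study procedure*.
2. In the closing table sentence, replace *medication* with *study procedure*, keeping the reference to 11.2.2.

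SAP 11.2.4 and Appendix I 1.2 need no change. The cost is two phrases and one table that Appendix I already presupposes. No new data are needed, because the procedure assessment is already collected and listed.

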11.2.6. Serious Adverse Events

Serious TEAEs will be summarized in a similar manner as described in Section 11.2.2. If a patient reported more than one serious TEAE with the same SOC or PT, the TEAE will be counted only once in that SOC or PT.

11.2.7. Adverse Events Leading to Death

TEAEs leading to death will be summarized in a similar manner as described in Section 11.2.2.

11.2.8. Missing and Partial AE Onset Dates

See appendix 1.2 for specific algorithms to impute missing start and stop dates

11.3. Vital Signs

The following Vital Signs measurements will be reported for this study:

- Supine Systolic Blood Pressure (mmHg)
- Supine Diastolic Blood Pressure (mmHg)
- Supine Pulse Rate (bpm)
- Respiratory Rate (breaths/min)

Vital signs data will be summarized at screening, and [when applicable] at each imaging visit prior to the administration of injection (florbetapir or flortaucipir), within 5 minutes after completion of injection, and at the completion of the imaging visit prior to discharge. Changes from baseline (prior to injection) to each follow-up will be calculated. All vital sign data will be summarized by enrolling diagnosis in a table, and listing for the Safety population.

11.4. Potentially Clinically Significant Results

Changes from baseline to all follow-ups in vital signs will be monitored for potentially clinically significance (PCS). Below are the criteria for PCS vital sign results.

Table 3: Potentially Clinically Significant Criteria

Parameter		Potentially Clinically Significant Criteria	
Vital Sign		Low	High
Systolic blood pressure	mmHg	≤ 90 and ≥ 20 decrease	≥ 180 and ≥ 20 increase
Diastolic blood pressure	mmHg	≤ 50 and ≥ 15 decrease	≥ 105 and ≥ 15 increase
Pulse rate	bpm	≤ 50 and ≥ 15 decrease	≥ 120 and ≥ 15 increase
Respiration rate	Breaths/min	≤ 10	

12. INTERIM ANALYSES

There is no interim analysis planned for this study.

APPENDIX I: ALGORITHMS TO HANDLE MISSING AND PARTIAL DATES**1.1.MISSING AND PARTIAL CONCOMITANT AND OTHER
MEDICATION START AND STOP DATES**

CONMED START DATE	CONMED STOP DATE	ACTION
Known	Known	If stop date < study med date, assign as prior If stop date ≥ study med date, assign as concomitant
	Partial	Impute stop date as latest possible date (i.e. last day of month if day unknown or 31 st December if day and month are unknown), then: If stop date < study med date, assign as prior If stop date ≥ study med date and start date, assign as concomitant
	Missing	If stop date is missing could never be assumed a prior medication
Partial	Known	Impute start date as earliest possible date (i.e. first day of month if day unknown or 1 st January if day and month are unknown), then: If stop date < study med date, assign as prior If stop date ≥ study med date and start date, assign as concomitant
	Partial	Impute start date as earliest possible date (i.e. first day of month if day unknown or 1 st January if day and month are unknown) and impute stop date as latest possible date (i.e. last day of month if day unknown or 31 st December if day and month are unknown), then: If stop date < study med date, assign as prior If stop date ≥ study med date and start date, assign as concomitant
	Missing	Impute start date as earliest possible date (i.e. first day of month if day unknown or 1 st January if day and month are unknown), then: If stop date is missing could never be assumed a prior medication
Missing	Known	If stop date < study med start date, assign as prior If stop date ≥ study med start date, assign as concomitant

CONMED START DATE	CONMED STOP DATE	ACTION
	Partial	Impute stop date as latest possible date (i.e. last day of month if day unknown or 31 st December if day and month are unknown), then: If stop date < study med date, assign as prior If stop date ≥ study med date, assign as concomitant
	Missing	Assign as concomitant

1.2.MISSING AND PARTIAL AE ONSET DATES

If the AE onset dates are missing, then the most conservative approach will be used to decide if the AE is TEAE or not, as detailed in the table below:

AE ONSET DATE/TIME	AE STOP DATE/TIME	ACTION
Partial, but known components show that it cannot be on or after an injection date/time and within 48 hours post-injection	Known	Not TEAE
	Partial	Not TEAE
	Missing	Not TEAE
Partial, could be on or after an injection date/time and within 48 hours post-injection	Known	
If stop date/time < flortaucipir (or florbetapir) injection date/time, then not TEAE
 
If stop date/time >= flortaucipir (or florbetapir) injection date/time, then TEAE

	Partial	
Impute stop date as latest possible date (i.e. 59 if minutes unknown or 23:59 if hours and minutes unknown; last day of month if day unknown or 31st December if day and month unknown), then:
 
If stop date/time < flortaucipir (or florbetapir) injection date/time, then not TEAE
 
If stop date/time >= flortaucipir (or florbetapir) injection date/time, then TEAE

AE ONSET DATE/TIME	AE STOP DATE/TIME	ACTION
	Missing	Assumed TEAE
Missing	Known	
If stop date/time < flortaucipir (or florbetapir) injection date/time, then not TEAE
 
If stop date/time >= flortaucipir (or florbetapir) injection date/time, then TEAE

	Partial	
Impute stop date as latest possible date (i.e. 59 if minutes unknown or 23:59 if hours and minutes unknown; last day of month if day unknown or 31st December if day and month unknown), then:
 
If stop date/time < flortaucipir (or florbetapir) injection date/time, then not TEAE
 
If stop date/time >= flortaucipir (or florbetapir) injection date/time, then TEAE

	Missing	Assumed TEAE

For the summarization of TEAEs by intensity, events recorded with missing intensity will be summarized as Severe.

For the summarization of TEAEs by seriousness, events recorded with missing seriousness will be summarized as Serious.

For the summarization of TEAEs by relationship to study drug or protocol procedure, events recorded with missing relationship will be summarized as Related.

APPENDIX II: SAS CODE TEMPLATE FOR ANALYSIS

1.1.SAMPLE CODE FOR EFFICACY ANALYSIS

1.1.1. DESCRIPTIVE STATISTICS

```
PROC MEANS data = <data>; class COGGRP;
output out= summ n=n_ mean=mean std=std median=median min=min max=max;
RUN;
QUIT;
```

```
PROC MEANS data = <data>; class FIGHTGRP;
output out= summ n=n_ mean=mean std=std median=median min=min max=max;
RUN;
QUIT;
```

1.1.2. HYPOTHESIS #1 AND #2

```
ods output contrasts=contrasts;
PROC GLM data = <data>;
class FIGHTGRP COGGRP;
model SUVR = FIGHTGRP COGGRP FIGHTGRP*COGGRP;
contrast "Active vs. Retired"      FIGHTGRP 1 -1;
contrast "CI vs. CN"              COGGRP 1 -1;
RUN;
QUIT;
```

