3.2. Sample Size Justification

No formal sample size calculation was performed. The study will stop enrolling subjects according to administrative consideration and decisions.

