10.1.2.1. Hypothesis #1: Difference in Quantitative Flortaucipir Uptake Between Cognitive Groups

The mean flortaucipir SUVr difference between cognitive statuses (cognitively impaired vs without cognitive or behavioural complaint) will be tested with the following hypothesis.

$$H_0 : \mu_{CI} = \mu_{CN}$$

$$H_A : \mu_{CI} \neq \mu_{CN} ,$$

Where:

- μ_{CI} is the mean flortaucipir SUVr in the cognitively impaired group
- μ_{CN} is the mean flortaucipir SUVr in the cognitive normal group

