10.1.2.2. Hypothesis #2: Difference in Quantitative Flortaucipir Uptake Between Fighter Groups

The mean flortaucipir SUVr difference between fighting groups (active vs retired) will be tested with the following hypothesis.

$$H_0 : \mu_{Act} = \mu_{Ret}$$

$$H_A : \mu_{Act} \neq \mu_{Ret} ,$$

Where:

- μ_{Act} is the mean flortaucipir SUVr in the active fighters
- μ_{Ret} is the mean flortaucipir SUVr in retired fighters

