10.1.3. Primary Analysis

Descriptive statistics for flortaucipir SUVr will be reported overall and by each enrolment group. Box-and-whisker plots of flortaucipir SUVr will be created to visually display tau distribution across these groups.

Hypotheses 1 and 2 will be tested using a two-way ANOVA, with fighters status (active or retired) and cognitive status (impaired or normal) as two main factors. The comparisons of mean SUVr values will be compared through setting up proper contrasts.

The descriptive statistics and ANOVA analysis will be summarized in a table and include the following:

- n
- Mean (SD)
- Median
- Min, Max
- Overall P-value from ANOVA
- P-values from each contrast

Hypotheses 3 and 4 will be tested using Fisher's exact test. The distributions for each enrollment group will be presented in a 4x2 contingency table along with the p-values from each test.

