10.1.3.1. Statistical Considerations in Primary Analysis

All hypothesis testing will be run at the 0.05 level of significance. Because this is a Phase I study, no correction for multiplicity will be applied to control for alpha.

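### The SAP code fits an interaction that section 10.1.3 neither names nor reports, so at the planned cell sizes the active-vs-retired contrast does not test the stated group means and has 12.5% more variance

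*SAP*

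**What the plan says.** - **Hypotheses.** SAP 10.1.2.1 and 10.1.2.2 state two-sided hypotheses about group means. For Hypothesis 1 the first parameter "is the mean flortaucipir SUVr in the cognitively impaired group"; for Hypothesis 2 it "is the mean flortaucipir SUVr in the active fighters".
- **Model in the text.** SAP 10.1.3 plans a two-way ANOVA "with fighters status (active or retired) and cognitive status (impaired or normal) as two main factors". The inferential results it lists are "Overall P-value from ANOVA" and "P-values from each contrast". It mentions no interaction term, test or p-value.
- **Model in the code.** Appendix II 1.1.2 has "model SUVR = FIGHTGRP COGGRP FIGHTGRP*COGGRP", followed by a 1, -1 contrast on each factor with no interaction coefficients given. The descriptive code in Appendix II 1.1.1 summarises SUVr separately by cognitive group and by fighter group, which gives raw group means.
- **Cell sizes.** The protocol synopsis plans about 10 impaired and 5 unimpaired among active fighters, and the same among retired fighters. SAP 3.2 gives no sample size calculation and says: "The study will stop enrolling subjects according to administrative consideration and decisions".
- **Use of the p-values.** SAP 10.1.3.1 says: "All hypothesis testing will be run at the 0.05 level of significance". SAP 10.1.2 labels all the tests exploratory. SAP 10.1.4 runs the fight-exposure correlations only if a contrast reaches p ≤ 0.15.

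**The concern.** A programmer following the text would most naturally fit main effects only; one following the template would fit four free cell means. The two models give different overall tests (2 df against 3 df) and, for Hypothesis 2, different contrasts. The plan does not say which is prespecified.

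The coded Hypothesis 2 contrast also differs from the parameter in SAP 10.1.2.2. It averages the impaired and unimpaired cells 1:1, while the fighter groups are planned 2:1. The results table could then show raw group means beside a p-value for a different mean difference. That p-value also feeds the p ≤ 0.15 gate for the exposure correlations, which bear on the primary objective about repetitive head trauma.

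**Working it through.** The plan states no power, SD or effect size, so there is no figure to reproduce. Variances below are in units of the within-cell variance σ². Cells are written as active impaired/unimpaired, retired impaired/unimpaired.

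**Inputs.** Planned cells 10/5, 10/5 (protocol synopsis; total 30); two-sided 0.05 (SAP 10.1.2 and 10.1.3.1). Assumed: equal within-cell variance, and the standard PROC GLM rule that unspecified interaction coefficients are spread equally over cells. The documents state neither.

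**Formulas.**
- Coded model: each contrast is a difference of unweighted cell averages, with variance ¼ × Σ(1/n) over the four cells.
- Main-effects model: variance 1 / Σ[n₁n₂/(n₁+n₂)]. The sum runs over the two cognitive strata for Hypothesis 2 and over the two fighter strata for Hypothesis 1.

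**Planned cells.**
- Coded, both contrasts: ¼ × (1/10 + 1/5 + 1/10 + 1/5) = 0.150.
- Main effects, Hypothesis 2: 1 / (10×10/20 + 5×5/10) = 1/7.5 = 0.133, which equals the raw 1/15 + 1/15.
- Main effects, Hypothesis 1: 1 / (10×5/15 + 10×5/15) = 1/6.667 = 0.150, which equals the raw 1/20 + 1/10.

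For Hypothesis 2 the variance ratio is 0.150/0.133 = 1.125, and the SE is 0.387 against 0.365 SD (ratio 1.061). From the noncentral t with 26 and 27 error df, the difference detectable with 80% power is 1.13 against 1.06 SD. Power at an assumed difference of 1 SD is 0.70 against 0.75. For Hypothesis 1 the estimate and its SE formula are the same in both models; only one error df is lost.

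**What is being tested.** Suppose, for illustration, that active and retired fighters differ by 1 SD among the impaired and not at all among the unimpaired. The stated group-mean difference is (10/15) × 1 = 0.67 SD. The coded contrast targets ½ × 1 = 0.50 SD.

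**Other splits of 30 (all assumed).**

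| Cells | Contrast | Coded | Main effects | Ratio |
|---|---|---|---|---|
| 12/3, 12/3 | H2 | 0.208 | 0.133 | 1.56 |
| 12/3, 12/3 | H1 | 0.208 | 0.208 | 1.00 |
| 14/1, 10/5 | H2 | 0.343 | 0.150 | 2.29 |
| 14/1, 10/5 | H1 | 0.343 | 0.234 | 1.46 |
| 2/13, 13/2 | H1 and H2 | 0.288 | 0.288 | 1.00 |

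At 14/1, 10/5 the detectable differences are 1.70 against 1.13 SD (Hypothesis 2) and 1.70 against 1.41 SD (Hypothesis 1). If one cell is empty, 1/n is undefined and the coded contrasts are not estimable. The main-effects contrasts still are, from the remaining complete stratum.

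**The case against.** The strongest reply is that there is no contradiction. A two-way ANOVA with two named factors does not exclude their interaction, and the template code may simply settle what the text leaves open. Protocol 8.1 also plans an ANOVA across the enrollment groups; if those are the four subgroups in the synopsis, the coded model supplies that 3-df overall test and a main-effects model does not. This stands in part. The text is incomplete rather than flatly contrary to the code, and the fix must keep a four-group test.

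Equal weighting of impaired and unimpaired fighters is also defensible, because the 2:1 mix is a recruitment target and not a stated population share. But SAP 10.1.2.2 states group means, and the plan nowhere says it intends equal weighting.

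Nor does the main-effects model always recover the raw group means. At 14/1, 10/5 it gives the unimpaired stratum a weight of 0.833/6.667 = 12.5%, while unimpaired fighters make up 1/15 (6.7%) of active and 5/15 (33.3%) of retired fighters. This also stands: with non-proportional cells the main-effects contrast is a precision-weighted adjusted difference.

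A reader might further infer that both contrasts lose precision, or that any imbalance costs a great deal. Neither follows. Hypothesis 1 loses nothing but one error df at the planned sizes, and the very uneven 2/13, 13/2 split loses nothing for either contrast.

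**Conclusion.** The text and code should be reconciled. At the planned cells the coded Hypothesis 2 contrast departs from the stated group means and has 12.5% more variance (6% in SE). Hypothesis 1 is unaffected there. The weighting changes the quantity tested only if an interaction exists; the loss of precision occurs either way.

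The larger losses (+129% for Hypothesis 2 and +46% for Hypothesis 1 at 14/1, 10/5) rest on an assumed split with a very small unimpaired cell. Approximate targets and an administrative stop make such a split possible, but nothing in the documents predicts it, so these figures show what could happen and are not the expected cost. The tests are exploratory and no power is claimed, so the practical impact is modest. The clearest consequences are an ambiguous prespecified model and a contrast p-value that gates later analyses.

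**What to change.** 1. In Appendix II 1.1.2, test both contrasts from `model SUVR = FIGHTGRP COGGRP;`.
2. Fit the interaction in a second model. From it, report the interaction p-value, the four cell means with confidence intervals, and the 3-df overall test across the four enrollment groups.
3. In SAP 10.1.3, name both models and say which one gives each reported p-value.

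The cost is one changed line of code, a second model call, and a few added results. The downside is small: if an interaction exists and the cells are non-proportional, the main-effects contrast is not exactly the raw group-mean difference, so it should be read alongside the interaction result.
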